Day/Week (Window)	Day -10 to -1	0*	Every 7 Days (±1 Day) Until Delivery		Day of Delivery (+2 Days)	Phone Call: 14 Days after Delivery (±3 Days)	Clinic Visit: 28 Days after Delivery (±3 Days)	
*Participants who early terminate from study drug should still continue with weekly visits through delivery, F1, and F2.
 
Some visits may be conducted as a home health or remote visit at the discretion of the investigator upon approval by the sponsor or designee and in accordance with local and regional regulations.
 
*See Section 8.1.8 for further details on timing of baseline visit.

CSS		X	X*	X	X		X	
To the extent possible, CSS assessments should be made by the same investigator or designee during study visits.
 
*At Week 3 visit only.

Other Procedures								
Health utilization		X		X			X	
Safety Procedures								
Drug and alcohol screen	X							
Physical examination	X	X	X	X	X		X	Complete examination conducted at screening and F2 visits. A symptom-directed examination focused on changes from last examination conducted at other visits. Includes confirmation of fetal cardiac activity via Doppler/auscultation at each visit while participant is pregnant.
Height	X							
Weight	X	X	X	X	X		X	

Visit Name	Screening	Treatment Period				Follow-Up		Notes
		Baseline	Weeks 1, 2, 3, etc.	Early Termination*	EOT/Delivery	F1	F2 (EOS)	
Day/Week (Window)	Day -10 to -1	0*	Every 7 Days (±1 Day) Until Delivery		Day of Delivery (+2 Days)	Phone Call: 14 Days after Delivery (±3 Days)	Clinic Visit: 28 Days after Delivery (±3 Days)	
*Participants who early terminate from study drug should still continue with weekly visits through delivery, F1, and F2.
 
Some visits may be conducted as a home health or remote visit at the discretion of the investigator upon approval by the sponsor or designee and in accordance with local and regional regulations.
 
*See Section 8.1.8 for further details on timing of baseline visit.

ECG	X							ECG is not a required study procedure; however, a local ECG at or after screening visit may be performed at the investigator's discretion.
Vital signs	X	X	X	X	X		X	
Hematology	X		X	X	X		X	
Chemistry	X		X	X	X		X	
Coagulation panel (PT/INR, PTT)	X		X	X	X		X	
Vitamin A, D, and E levels		X	X*		X		X	*Every 4 weeks, starting with Week 4 visit. The sample collection tube should be protected from light.
Urinalysis	X	X	X	X	X		X	
Lipid panel, glycated albumin	X		X*		X		X	*Every 2 weeks, starting with Week 2 visit

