This study assesses the primary efficacy endpoint at 3 weeks because it is clinically relevant as a timeframe within which demonstrated efficacy of a drug for ICP will be important for clinical decision making. In a large population-based, case-control study (Geenes et al. 2014), 669 patients with a singleton pregnancy were identified within the UK Obstetric Surveillance System (UKOSS) as having severe ICP; the mean gestational age was 33 weeks 4 days at time of diagnosis in these patients. Additionally, in a recent double-blind, multicenter, randomized placebo-controlled study that enrolled 605 women with ICP in the United Kingdom (Chappell et al. 2019), the median gestational age was 34.4 weeks at randomization. With the mean/median gestational ages at diagnosis occurring between 33 and 34 weeks—and with Royal College of Obstetricians and Gynaecologists (RCOG) guidelines (2011) recommending consideration of elective delivery for patients with ICP after 37 weeks based on sBA-related risks of stillbirth—approximately 3 weeks of study drug treatment corresponds to a timeframe within which demonstration of sBA reduction is expected to be impactful for clinical decision making. Furthermore, based on clinical experience with another IBAT inhibitor (maralixibat),

continued improvements in sBA are likely to be seen with relatively longer treatment durations, arguing against analysis of sBA prior to the 3-week timeframe as a primary efficacy endpoint. In Study LUM001-501, decreases in both sBA and ItchRO (observer) were observed at Week 2 and continued to decline even further at Week 4 in pediatric participants with non-truncating PFIC2, supporting the benefit of treatment durations >2 weeks for reduction of sBA and pruritus. However, given the mean/median gestational ages for ICP diagnosis (33–34 weeks), along with the requirement for randomization no later than 36 weeks 0 days in Part 2, participants are relatively more likely to be at the upper range of gestational age eligibility in this study, and as such, relatively few participants in this study will be expected to remain on treatment beyond 3 weeks.

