## 7.2. Participant Withdrawal from Study

A participant may withdraw from the study at any time for any reason without prejudice to future medical care by the physician or at the institution. The sponsor or designee may discontinue the participant from the study at any time. If an investigator determines that a participant's discontinuation from study is warranted, such action should be discussed with the sponsor or designee, when possible, in advance of the discontinuation. The reason for termination and the date of stopping study drug must be recorded in source documents.

Participants who discontinue from the study for safety reasons are followed as long as clinically indicated or until a safety finding is considered to be permanent.

Participants who discontinue from the study will not be replaced.

If a participant withdraws consent for disclosure of future information, the sponsor may retain and continue to use any data collected before such a withdrawal of consent.

A participant who withdraws from the study may request destruction of any samples taken and not tested, and the investigator must document this in the site study records.

The reason for termination and the date of stopping study drug must be recorded in source documents. The evaluations listed for the early termination visit are to be performed as completely as possible for any participant who discontinues from study participation.

Data to be collected at the time of study discontinuation and follow-up and for any further evaluations that need to be completed are outlined in the SoA (Table 1).

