#### **9.2.7. Events of Clinical Interest**

ECIs will include CTCAE Grade  $\geq 3$  diarrhea, CTCAE Grade  $\geq 3$  abdominal pain, CTCAE Grade  $\geq 3$  transaminase increases, and fat-soluble vitamin deficiency; these will be subject to specialized, targeted data collections. Please refer to [Appendix 3](#) for algorithms to assess transaminase increases and/or potential DILI events.

Additional ECIs may be identified during the course of the study.

Specifics regarding events to be designated as ECIs, along with reporting instructions/timelines, will be included in the eCRF completion guidelines. ECIs that meet seriousness criteria shall be subject to expedited reporting as outlined in [Sections 9.2.1](#) and [9.2.5](#).

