##### **10.4.2.1. Adverse Events**

In general, TEAEs are defined as AEs that start or deteriorate on or after the first dose of study medication and no later than 7 days following the last dose of study medication. For any participants (i.e., expectant mothers) who die during the study and the date of death is between the date of the first dose of study medication and the date of study discontinuation (as entered by the site), inclusive, all AEs (including those resulting in death) that occur during the study will be considered as TEAEs irrespective of the last dose and will be included in the TEAE summaries. All summaries of AEs will be based on TEAEs unless specified otherwise.

The complete list of Preferred Terms for AESIs and ECIs (as described in [Sections 9.2.6](#) and [9.2.7](#)) will be outlined in the SAP and summarized.

AEs will be coded using MedDRA. The number and proportion of participants who experience the event according to MedDRA System Organ Class (SOC) and Preferred Term will be presented by treatment group.

The incidence of all AEs and treatment-related AEs will be tabulated by treatment received. These AEs will be classified by SOC and Preferred Term using MedDRA. AEs will be graded using the CTCAE, Version 5.0, grading scale. For incidence reporting, if a participant reported >1 AE that was coded to the same SOC or Preferred Term, the participant will be counted only once for that specific SOC or Preferred Term. An overview of AEs and TEAEs, both of which include participant incidence of AEs, treatment-related AEs, AEs by severity, AESIs, ECIs, SAEs, deaths, and AEs that lead to discontinuation, will be presented.

Furthermore, exposure-adjusted incidence rates (EAIR) will be provided for each AE reported. For EAIR analyses, the following convention will be used to calculate the denominator (i.e., population-level time at-risk) for these analyses. The population-level time at-risk includes only the time each participant is at risk. The start date of at-risk time is the date of first dose of study drug, and the last date of at-risk time is the start date of the occurrence of the AE or is censored at completion/early termination, whichever is earlier.

While no formal hypothesis testing or margin selection is planned, the risk difference and corresponding exact 95% CI (using the method of Chan and Zhang [1999]) will be presented to compare treatment groups with regards to AESIs and ECIs.

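### Vitamins A, D and E are not drawn at Early Termination, so a woman who stops drug before about Day 21 can lack an A/D/E sample in the 7-day safety window

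*Protocol*

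**What the plan says.** The row "Vitamin A, D, and E levels" in protocol Table 1 is marked at baseline, at the weekly visits, at EOT/Delivery and at F2. Its note limits the weekly-visit draws: "Every 4 weeks, starting with Week 4 visit. The sample collection tube should be protected from light". The Early Termination cell is empty. Hematology, chemistry, coagulation and urinalysis are all marked in that column. SAP Table 7 repeats the pattern.

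Protocol 9.2.7 closes its list of ECIs with "and fat-soluble vitamin deficiency; these will be subject to specialized, targeted data collections". ECIs belong to the Part 1 primary endpoint (protocol 3.1) and the Part 2 safety endpoint (3.3). Protocol 10.4.2.1 and SAP 7.1.7 plan a risk difference with exact 95% CI for them.

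Protocol 10.4.2.1 defines TEAEs as events that begin or worsen "on or after the first dose of study medication and no later than 7 days following the last dose of study medication", and makes TEAEs the default basis for AE summaries. SAP 7.1.5.1 says the same for mothers. SAP 7.2 ends laboratory summaries at the same point for women who have permanently stopped drug.

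Women who stop drug remain under observation: "Participants who early terminate from study drug should still continue with weekly visits through delivery, F1, and F2" (Table 1). For those who leave the study, protocol 7.2 says: "The evaluations listed for the early termination visit are to be performed as completely as possible".

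**The concern.** A woman treated up to delivery has vitamins measured as treatment ends. A woman who stops earlier waits for the next 4-weekly visit or for delivery, and by then the 7-day window may have closed. A woman who leaves the study gets the early termination evaluations, which include no vitamin draw.

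The plan treats fat-soluble vitamin deficiency as an event to be watched and compared between arms. Protocol 6.8.1.1 describes gastrointestinal effects as common with this drug class, so early stopping could fall more heavily on volixibat. If it does, the thinner sampling would also fall more heavily on that arm.

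**Working it through.** The plan states no figure for this coverage, so there is none to reproduce. The check is a count over the visit schedule.

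**Inputs**
- Vitamin draws after baseline: Days 28, 56, ... before delivery, then delivery (Table 1). Day 0 is the first dose, as in the protocol.
- Window: last dose + 7 days (protocol 10.4.2.1; SAP 7.1.5.1 and 7.2).
- Time to delivery, T days: the protocol's endpoint rationale cites a median entry of 34.4 weeks in an earlier trial. Delivery at 37 weeks gives 2.6 × 7 ≈ 18 days. Delivery at 39 weeks (the planned birth mentioned in protocol 8.1.12 for bile acids below 100) gives 4.6 × 7 ≈ 32 days. The same rationale says "relatively few participants in this study will be expected to remain on treatment beyond 3 weeks".
- Stopping day s: the documents give no distribution. **Assumption:** uniform over Days 1 to T − 1.

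**Step 1: the cut-off.** The Week 4 draw is in the window only if s + 7 ≥ 28, that is s ≥ 21. With the ±1 day visit window the cut-off is Day 20 to Day 22. The delivery draw is in the window only if s ≥ T − 7.

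**Step 2: share without a sample.** Two definitions are shown: (a) no A/D/E sample from first dose to last dose + 7 days; (b) none from last dose to last dose + 7 days. For T ≤ 28 they agree and equal (T − 8)/(T − 1). For T > 28, (a) equals 20/(T − 1), because anyone stopping on Day 21 or later has the Week 4 sample. Definition (b) is counted day by day.

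| T (days) | (a) first dose to last dose + 7 | (b) last dose to last dose + 7 |
|---|---|---|
| 14 | 6/13 = 46% | 46% |
| 18 | 10/17 = 59% | 59% |
| 21 | 13/20 = 65% | 65% |
| 28 | 20/27 = 74% | 74% |
| 32 | 20/31 = 65% | 65% |
| 35 | 20/34 = 59% | 59% |
| 42 | 20/41 = 49% | 26/41 = 63% |
| 56 | 20/55 = 36% | 40/55 = 73% |
| 126 | 20/125 = 16% | 86/125 = 69% |

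**Step 3: visit tolerance.** With Week 4 one day late and the delivery draw two days late, (b) becomes 62% at T = 14 and 81% at T = 28. With Week 4 one day early, (b) at T = 32 is 19/31 = 61%.

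**Step 4: very early stops.** For stops in the first 14 days with T of 28 or more, the share is 100% under either definition, since 14 + 7 = 21 < 28.

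**Step 5: leaving the study.** Before Week 4 only the baseline draw has been taken, and the Early Termination column adds none. Such a woman may have no post-baseline A/D/E value.

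**The case against.** The strongest reply is that a missing sample is not the same as a missing event.

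- The TEAE rule turns on when an event starts or worsens, not when it is found. SAP 7.1.5.2 also leans towards inclusion when onset dates are partial or missing. A reader might infer that a deficiency first seen after the 7 days cannot be counted. The documents do not say so: it drops out only if onset is dated after the window, for example to the day of the draw.
- SAP Appendix 2 puts vitamin K and INR terms in the same ECI, and PT/INR is drawn weekly and at Early Termination. A reader might infer that early stoppers have almost no chance of being counted. That is too strong, because only the A, D and E part is affected and some stoppers are sampled in time.
- Women who stop drug keep their Week 4, delivery and F2 draws. Late findings are listed (SAP 7.1.6.1) and can enter the protocol's overview of all AEs. Protocol 10.4.2.3 summarises out-of-range values at any post-baseline assessment, although SAP 7.2 narrows this.
- Few may stop early. Protocol 4.4 reports no discontinuation for diarrhea or cramping in the healthy-volunteer study and expects mild, transient gastrointestinal effects here.
- The lipid and glycated albumin row is also blank at Early Termination, so the omission may be deliberate for less frequent panels. Protocol Appendix 1 also allows extra tests at any time.

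All of this limits the consequence. None of it schedules an A/D/E sample near the last dose of an early stopper, and lipids, unlike these vitamins, are not an ECI.

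**Conclusion.** The gap is real and modest. It concerns vitamins A, D and E, in women who stop before about Day 21 and deliver more than 7 days after the last dose, and in those who leave the study before Week 4. The 46-74% range rests on the uniform stopping day and on 14-42 days to delivery. For longer treatment the result depends on the definition: if any on-treatment sample counts, most women are covered.

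Two further inferences are not supported. Three quarters is not a typical figure: it is close to the top of the range and is reached only when delivery falls near Day 28. Nor can the number of lost cases, or the bias in the between-arm risk difference, be stated. The documents give no discontinuation rate, no deficiency rate, and no evidence that deficiency is more frequent in women who stop early. The supportable conclusion is possible under-ascertainment of the A/D/E component, of unknown size, which a small schedule change would largely close.

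**What to change.** Mark vitamins A, D and E in the Early Termination column of protocol Table 1 and SAP Table 7, taken at the blood draw already scheduled for hematology, chemistry and coagulation. The share without a sample then falls to those who miss that visit or attend it more than 7 days after the last dose. SAP Table 5 already assigns Study Days 2 to 43 to the Week 4 vitamin visit, so samples taken in that period need no new analysis window.

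The cost is one extra light-protected tube and assay per early stopper.

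The 7-day limit should stay. Waiving it for the first sample after stopping would apply to early stoppers alone, while the F2 samples of women treated to delivery, 28 days after birth, stayed outside the window. Ascertainment would become unequal, and off-drug events would enter the comparison.

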## LIST OF ABBREVIATIONS

Abbreviation	Definition
7 $\alpha$ C4	7 $\alpha$ -hydroxy-cholesten-3-one
ACE	angiotensin-converting enzyme
AE	adverse event
AESI	adverse event of special interest
ANCOVA	analysis of covariance
BID	twice daily
BMI	body mass index
BPP	biophysical profile
C max	maximum observed concentration
CMH	Cochran Mantel Haenszel
CRL	crown-rump length
CRO	contract research organization
CSS	Clinician Scratch Scale
CTCAE	Common Terminology Criteria for Adverse Events
CTG	cardiotocography
DART	developmental and reproductive toxicology
DILI	drug-induced liver injury
ECI	event of clinical interest
eCRF	electronic case report form
eDiary	electronic diary
EQ-5D-5L	EuroQol 5-dimension 5-level
F2	follow-up Visit 2
fBA	fecal bile acid
GCP	Good Clinical Practice
GI	gastrointestinal
HBsAg	hepatitis B surface antigen
HCV	hepatitis C virus
IB	Investigator's Brochure
IBAT	ileal bile acid transporter
ICF	informed consent form
ICH	International Council for Harmonisation of Technical Requirements for Pharmaceuticals for Human Use
ICP	intrahepatic cholestasis of pregnancy

Abbreviation	Definition
IDMC	independent data monitoring committee
IEC	independent ethics committee
INR	international normalized ratio
IRB	institutional review board
IRT	interactive response technology
ItchRO	Itch Reported Outcome
IV	intravenous
JAK	Janus kinase
LDL	low-density lipoprotein
LLOQ	lower limit of quantitation
LS	least squares
MAR	missing at random
medical monitor	sponsor or CRO medical monitor
MI	multiple imputation
mITT	modified intent-to-treat
MMRM	mixed-effects model for repeated measures
MNAR	missing not at random
NASH	nonalcoholic steatohepatitis
NICU	neonatal intensive care unit
NRS	numerical rating scale
NST	nonstress test
OR	odds ratio
PBC	primary biliary cirrhosis
PD	pharmacodynamic
PFIC	progressive familial intrahepatic cholestasis
PGIC-Itch	Patient Global Impression of Change-Itch
PIS-Itch	Patient Impression of Severity-Itch
PK	pharmacokinetic
PPAR	peroxisome proliferator-activated receptor
PPROM	preterm premature rupture of the membranes
PRO	patient-reported outcome
PROMIS ®	Patient-Reported Outcomes Measurement Information System
PSC	primary sclerosing cholangitis
QD	once daily
QTcF	QT interval corrected using Fridericia's correction formula

Abbreviation	Definition
RCOG	Royal College of Obstetricians and Gynaecologists
SAE	serious adverse event
SAP	statistical analysis plan
sBA	serum bile acid
SF	Short Form
SoA	schedule of activities
SOC	System Organ Class
TEAE	treatment-emergent adverse event
T max	time to reach C max
UDCA	ursodeoxycholic acid
WI-NRS	Worst Itch Numeric Rating Scale

## 2. INTRODUCTION

### 2.1. Background on Intrahepatic Cholestasis of Pregnancy

Intrahepatic cholestasis of pregnancy (ICP) is a rare cholestatic disorder that occurs during pregnancy and is associated with maternal changes in liver function, elevated levels of serum bile acids (sBAs), and intractable pruritus, as well as adverse perinatal outcomes ([EASL 2009](#); [Geenes and Williamson 2009](#); [Williamson and Geenes 2014](#); [Ozkan et al. 2015](#); [Wood et al. 2018](#)). Cholestasis refers to an impairment of bile secretion and/or bile flow, which may clinically present with symptoms such as pruritus, fatigue, and jaundice and may be associated with changes in liver biochemistry markers. Intrahepatic cholestasis is defined as cholestasis resulting from hepatocellular functional defects or obstructive lesions of the intrahepatic biliary tract distal from bile canaliculi.

ICP is characterized by pruritus, which is frequently intense and intractable, with typical onset in the second or third trimester of pregnancy and elevated serum aminotransferases and sBA levels. ICP is also frequently associated with an abnormal maternal metabolic profile. In addition to the hepatic features, there is an increased prevalence of dyslipidemia and impaired glucose tolerance in patients with ICP ([Martineau et al. 2015](#)). Gestational diabetes and preeclampsia also occur more commonly in women with ICP ([Goulis et al. 2004](#); [Martineau et al. 2014](#)). After delivery, there is rapid (within a few weeks) resolution of signs and symptoms.

ICP is also associated with an increased risk for adverse perinatal outcomes, including preterm birth and life-threatening or even fatal consequences for the fetus, such as stillbirth ([Sepulveda et al. 1991](#); [Williamson et al. 2001](#); [Ovadia et al. 2019](#)).

Although ICP resolves rapidly following delivery, it is associated with an increased risk of future morbidity, including higher incidence of hepatobiliary diseases such as hepatitis, fibrosis, and gallstones and increased risk of liver and biliary tree cancer, immune-mediated disease, and cardiovascular disease. Moreover, oral contraceptives, in particular those containing estrogens, may cause recurrence of symptoms, and guidelines recommend the use of alternative methods of contraception ([Bicocca et al. 2018](#)). Furthermore, patients with ICP can suffer from jaundice or present with vitamin K deficiency, which can lead to prolonged coagulation time and increase the risk of intrapartum and postpartum hemorrhage ([Mohan et al. 2019](#)).

Generally speaking, ICP is diagnosed if sBA levels are approximately  $\geq 10$   $\mu\text{mol/L}$  in a pregnant woman with new onset of pruritus during pregnancy and no other known pathology thought to be responsible for the laboratory findings and/or symptoms ([Bicocca et al. 2018](#)). ICP can be classified as mild or severe depending on the level of accumulation of sBA, with 40  $\mu\text{mol/L}$  often used as the threshold value that is considered severe ([Bicocca et al. 2018](#)).

### 2.2. Study Rationale

The pathophysiology of ICP in the mother is incompletely understood; however, there is extensive clinical evidence that elevated maternal sBA levels are linked to maternal and fetal morbidity and mortality associated with ICP, suggesting that elevated maternal sBA plays a causal role in these adverse clinical outcomes ([Sepulveda et al. 1991](#); [Williamson et al. 2001](#); [Glantz et al. 2004](#); [Geenes et al. 2014](#); [Mohan et al. 2019](#); [Ovadia et al. 2019](#)).

The pathophysiology of adverse perinatal outcomes in ICP is likely related to the elevated sBA levels in the expectant mother (Ovadia et al. 2019). In pregnancies uncomplicated by ICP, a physiologic sBA gradient across the placenta facilitates the disposal of fetal bile acids into the maternal blood stream, with ultimate elimination of both maternal and fetal bile acids via maternal feces (Monte et al. 1995). However, in ICP, elevated sBA levels on the maternal side cause a reduction or reversal of the physiologic transplacental gradient, resulting in the accumulation of bile acids in the fetal compartment, as evidenced by the detection of elevated levels in amniotic fluid, cord serum, and meconium (Shaw et al. 1982; Geenes and Williamson 2009; Williamson and Geenes 2014). Increased bile acid concentrations are associated with toxic effects, such as fetal cardiac arrhythmia and placental vessel spasms (Sepulveda et al. 1991; Williamson et al. 2001). Such effects can have potentially life-threatening or even fatal consequences for the fetus, and data from in vitro and animal studies support the role of elevated levels of bile acids in the promotion of preterm labor and the cause of the presence of meconium in the amniotic fluid, neonatal respiratory distress, and stillbirth (Geenes et al. 2014; Williamson and Geenes 2014). Several cohort studies as well as recent systematic reviews with meta-analyses have clearly demonstrated the increased risk of adverse perinatal outcomes in ICP and their correlation with maternal sBA levels (Glantz et al. 2004; Geenes et al. 2014; Mohan et al. 2019; Ovadia et al. 2019):

- The risk of stillbirth has been shown to increase in women with ICP who have sBA concentrations >100 µmol/L and increases as gestation progresses (Ovadia et al. 2019), suggesting a likely benefit from reduction of sBA promptly upon detection of elevated levels.
- In a large prospective population-based case-control study performed in the United Kingdom, which included 669 women with severe ICP (sBA ≥40 µmol/L at any time during pregnancy) and a singleton pregnancy, a doubling in sBA level increased the risk of all preterm delivery by 68%, of spontaneous preterm delivery by 66%, of meconium staining of the amniotic fluid by 55%, and of stillbirth by 200% (Geenes et al. 2014).

Increased bile acid concentrations appear to play a primary role in the development of the characteristic cholestatic pruritus associated with ICP, which is typically clinically significant, and in some cases is an indication to iatrogenic preterm delivery (Chappell et al. 2019). The link is complicated by how specific hydrophilic and hydrophobic subspecies may interplay in pruritus. It is possible, however, that a certain profile of sBA and/or pruritogen(s) is necessary to mediate pruritus (Bergasa 2014). However, accumulation of bile acid as a result of cholestatic liver disease, including ICP, has been associated with pruritus, although direct correlation of sBA levels to severity of itch is debatable (Pathak et al. 2010; Kremer et al. 2012). This association of sBA and pruritus is further supported by evidence from pregnancies in other cholestatic conditions. In pregnant women with non-ICP-induced intrahepatic or extrahepatic cholestasis, such as primary biliary cirrhosis (PBC) and primary sclerosing cholangitis (PSC), respectively, in which systemic bile acid concentrations are typically elevated, similar maternal and fetal morbidity and mortality are observed (Efe et al. 2014; Patel et al. 2019). Based on the collective data, the elevation of sBA plays a direct causal role on the characteristic maternal and fetal pathology of ICP.

